7.1 Interim Analysis and Early Stopping Guidelines

No formal interim safety analysis is planned for this study (Refer to protocol section 10.3.1).

7.2 Primary Analysis

The primary analysis will occur after the database lock following the last subject's last visit.

7.3 Final Analysis

The primary analysis will be the final analysis.

8. Data Screening and Acceptance

8.1 General Principles

The objective of the data screening is to assess the quantity, quality, and statistical characteristics of the data relative to the requirements of the planned analyses.

8.2 Data Handling and Electronic Transfer of Data

The Amgen Global Study Operations-Data Management (GSO-DM) department will provide all data to be used in the planned analyses. This study will use the RAVE database. The database will be subject to edit checks outlined in the Clinical Data Management Plan (DMP). See details of this section in the DMP.

8.3 Handling of Missing and Incomplete Data

Incomplete data in the Primary Endpoints will be excluded from analysis. The number and frequency of missing values will be reported in the final study report. Imputation for missing or incomplete dates will be performed, if required. If imputed dates are used, they will be identified as such in the final study report. PK concentrations below the lower limit of quantification will be set to zero. Details of the imputation algorithm are provided in [Appendix A](#).

8.4 Detection of Bias

Lack of protocol compliance and the potential for biased statistical analyses will be examined by assessing the incidence of important protocol deviations in each group. The clinical study team will identify and document the criteria for important protocol deviations.

8.5 Outliers

All confirmed outlier data will be included in the analyses presented in this statistical analysis plan unless there is sufficient scientific justification to exclude them.

Pharmacokinetic (PK) concentration data will be evaluated for outliers by visual inspection, and decisions to re-assay individual samples will be made in accordance with standard pharmacokinetic evaluation practice.

8.6 Distributional Characteristics

Where appropriate, the assumptions underlying the proposed statistical methodologies will be assessed. If required data transformations or alternative non-parametric methods of analyses will be utilized.

8.7 Validation of Statistical Analyses

Programs will be developed and maintained, and output will be verified in accordance with current risk-based quality control procedures.

Tables, figures, and listings will be produced with validated standard macro programs where standard macros can produce the specified outputs.

The production environment for statistical analyses consists of Amgen-supported versions of statistical analysis software; for example, the SAS System version 9.3 or later.

9. Statistical Methods of Analysis

9.1 General Considerations

Descriptive statistics will be provided for selected demographics, adverse events, vital signs, ECG, PK, and laboratory measurements. Descriptive statistics on continuous data will include means, medians, standard deviations, and ranges, while categorical data will be summarized using frequency counts and percentages. Graphical summaries of the data may also be presented. When data are summarized by time, the values recorded against the scheduled time points listed in the protocol will be used. When assessing minimum/maximum increases or decreases over the study, all assessments, including unscheduled assessments will be used. All data analysis will be conducted using subjects in the safety analysis set except for pharmacokinetic analysis, which will be conducted using PK analysis set. For statistical analyses comparing change from baseline, only subjects with both baseline and at least one post-baseline assessment will be included. The primary analysis will occur after the database lock following last subject last visit.

9.2 Subject Accountability

The number and percent of subjects who were enrolled, received investigational product, completed study, discontinued the study (including reasons for discontinuing) will be

summarized by group. Key study dates for the first subject enrolled and last subject's end of study will be presented. A subject listing and summary noting inclusion in each analysis subset will be reviewed for all subjects enrolled. A subject listing noting reason for discontinuing the study and a list of subjects screened but not enrolled (screen failures) will be reviewed.

9.3 Important Protocol Deviations

Important Protocol Deviations (IPDs) categories are defined by the study team before the first subject's initial visit and updated during the IPD reviews throughout the study prior to database lock. These definitions of IPD categories, subcategory codes, and descriptions will be used during the course of the study. Eligibility deviations are defined in the protocol. Eligibility deviations that are defined as IPDs will be summarized in both the IPD and Eligibility Deviation table and IPD and Eligibility Deviation listings.

9.4 Demographic and Baseline Characteristics

Summary statistics of the demographic and baseline characteristics will be tabulated using the Safety Analysis Set for both the study groups. The demographic characteristics include age, sex (male versus female), race and ethnicity. The baseline characteristics will be vital signs (blood pressure, heart rate, respiratory rate, and oral temperature), physical examinations (height, weight, BMI), ECG parameters, and selected laboratory parameters.

9.5 Efficacy Analyses

No efficacy analysis is applicable for this study.

9.6 Safety Analyses

9.6.1 Adverse Events

The Medical Dictionary for Regulatory Activities (MedDRA) version 20.1 will be used to code all events categorized as adverse events (AE) to a system organ class and a preferred term. The CTCAE version 4.0 will be used to grade severity of adverse events unless specified otherwise. Treatment-emergent adverse events are events with an onset after the administration of the first dose of investigational product.

The subject incidence of adverse events will be summarized for all treatment-emergent adverse events, serious adverse events, and fatal adverse events.

Subject incidence of all treatment-emergent adverse events, serious adverse events, adverse events leading to withdrawal of investigational product, and fatal adverse events will be tabulated by system organ class and preferred term in alphabetical order.

Subject incidence of events of interest (standardized MedDRA queries and/or Amgen customized queries) will also be summarized according to their categories and preferred term. Summaries of treatment-emergent and serious adverse events will be tabulated by system organ class, preferred term, and grade.

9.6.2 Laboratory Test Results

Analyses of laboratory values will include summary statistics over time (for each protocol scheduled visit) for selected laboratory analytes in Table 3 of the protocol by group.

Additional summaries may include descriptive statistics of changes from baseline over time, change from baseline to the post dose maximum, time to post-dose maximum, change from baseline to the post-dose minimum and the time to the post-dose minimum. Shift tables based on CTCAE grading may be provided for select analytes.

9.6.3 Vital Signs

Subject-level data for vital signs including blood pressure, heart rate, respiratory rate, and body temperature will be presented and reviewed for each subject. The analyses of vital signs will include summary statistics over time (for each protocol scheduled study visit) by group. Depending on the size and scope of changes, summaries of changes from baseline over time may be provided.

9.6.4 Electrocardiogram

All on-study ECG data will be reviewed and may be plotted. Summaries over time and/or changes from baseline over time will be provided for all ECG parameters (e.g., RR, PR, QRS, QTc). Subjects' maximum change from baseline in QTcF will be categorized and the number and percentage of subjects in each group will be summarized. Subjects' maximum post-baseline values will also be categorized and the number and percentage of subjects in each group will be summarized. Baseline ECG recording is defined as the mean of the 3 sets of triplicate ECG results at day 1 pre-dose (a total of 9 assessments).

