End of Study	defined as the date when the last subject is assessed or receives an intervention for evaluation in the study (ie, last subject last visit), following any additional parts in the study (eg, long-term follow-up), as applicable
End of Study for Individual Subject	defined as the last day that protocol-specified procedures are conducted for an individual subject
End of Treatment	defined as the last assessment for the protocol specified treatment phase of the study for an individual subject
Enrollment	when the investigator decides that the subject has met all eligibility criteria
GCP	good clinical practice
GMR	geometric mean ratio
HBcAb	hepatitis B core antibody
HbsAg	hepatitis B surface antigen
hERG	human Ether-a-go-go-Related Gene
HepCab	hepatitis C antibody
HF	heart failure

Approved

Abbreviation or Term	Definition/Explanation
HFpEF	heart failure with preserved ejection fraction
HFrfEF	heart failure with reduced ejection fraction
HIV	human immunodeficiency virus
HR	heart rate
ICF	informed consent form
ICH	international conference on harmonization
IP	investigational product
IPIM	investigational product instruction manual
IUD	intrauterine device
IV	Intravenous
MDRD	modification of diet in renal disease
NOAEL	no-observed-adverse-effect-level
NOEL	no-observed-effect-level
P-gp	P glycoprotein
PK	Pharmacokinetics
PR Interval	pr interval is measured from the beginning of the P wave to the beginning of the QRS complex in the hearts electrical cycle as measured by ECG
Primary Completion	defined as the date when the last subject is assessed or receives an intervention for the final collection of data for the primary endpoint(s), for the purposes of conducting the primary analysis, whether the study concluded as planned in the protocol or was terminated early
QRS Interval	qrs interval is the interval between the Q wave and the S wave in the heart's electrical cycle as measured by ECG; represents the time it takes for the depolarization of the ventricles
QT interval	qt interval is a measure of the time between the start of the Q wave and the end of the T wave in the heart's electrical cycle as measured by ECG
QTc interval	qt interval corrected for heart rate using accepted methodology
QTcF	qt interval corrected for heart rate using Fridericia's formula
RI	renal impairment
RR	respiratory rate
SAE	serious adverse event

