2.3 Risk Assessment

AMG 986 has an identified risk of embryo-fetal toxicity. AMG 986 caused embryo-fetal toxicity in nonclinical developmental and reproductive toxicology studies in 2 different species. Oral administration of AMG 986 resulted in abortions in rabbits and fetal skeletal and tail abnormalities in rats. Women of childbearing potential are not eligible to participate in this study, and male subjects must agree to practice an acceptable method of effective birth control and refrain from sperm donation while on study and through 11 weeks after receiving the last dose of AMG 986. These inclusion/exclusion criteria will prevent pregnancy and mitigate the risk of embryo-fetal toxicity.

AMG 986 has a potential risk of causing changes in blood pressure. AMG 986 is expected to positively stimulate the endogenous apelin-dependent pathways, which include vasodilation. Therefore, expected acute risks associated with AMG 986 are of a cardiovascular nature, such as hypotension, although other effects, such as tachycardia or even hypertension cannot be excluded.

Overall, the nonclinical (toxicology and safety pharmacology) package suggests a safe profile at the doses planned in clinical trials with AMG 986. Genetic toxicology and photosafety evaluations indicated that AMG 986 is not genotoxic or phototoxic. No AMG 986-related toxicity was identified in the rat or dog toxicology studies that were conducted with oral (28-day studies) or IV (14-day studies) dose administration. The AUC exposure margins based on NO(A)EL doses from the rat and dog toxicology studies support the planned clinical dose range. Additionally, no AMG 986-related effects in the safety pharmacology studies were identified, and data indicate that QTc interval prolongation risk is low.

Developmental and reproductive toxicology studies identified a risk for embryo-fetal toxicity as described above.

As of 14 March 2017, safety and tolerability data on clinical exposure to AMG 986 from FIH study 20150183 (a randomized, placebo controlled, double-blind, single day ascending dose and multiple daily ascending dose study) were available and reviewed for 9 fully implemented cohorts of 8 healthy subjects each. The subjects reviewed included those who received single oral doses of AMG 986 up to 200 mg, oral doses of 5 mg of AMG 986 for 7 consecutive days, as well as IV doses of AMG 986 over 24 hours

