4.2 Exclusion Criteria

Exclusion Criteria for All Subjects:

201. Subjects whose second MDRD eGFR result on day -1 is not within 15% of the first eGFR result performed during the screening period. Healthy volunteers who have normal renal function, but show a difference greater than 15% in eGFR based on MDRD during the screening period, will be included in the trial at the discretion of the investigator and the sponsor after a 24-hour creatinine clearance has been performed that meets eligibility criteria.
202. Subjects who are the recipient of a renal transplant and/or are on immunosuppressants.
203. Subjects with a history of hospitalization for heart disease or angina within 4 months of screening.
204. Current or prior malignancy within 5 years of enrollment with the exception of non-melanoma skin cancers, cervical or breast ductal carcinoma in situ, and adenocarcinoma of the prostate Stage I or IIa (defined as T1, T2a or T2b, N0-, M0 with documented serum PSA < 20 ng/mL and Gleason score ≤ 7) per the American Joint Committee on Cancer (AJCC) primary tumor, regional lymph nodes, and distant metastasis system.
205. Positive for human immunodeficiency virus (HIV antibodies), hepatitis B surface antigen (HBsAg) or hepatitis C virus antibodies (HepCAb) at screening
206. Subject has known sensitivity to any of the products or components to be administered during dosing.

207. Subject likely to not be available to complete all protocol-required study visits or procedures (including the research facility residency period), and/or to comply with all required study procedures to the best of the subject and investigator's knowledge.
208. History or evidence of any other clinically significant disorder, condition or disease with the exception of those outlined above that, in the opinion of the investigator or Amgen physician, if consulted, would pose a risk to subject safety or interfere with the study evaluation, procedures or completion.
209. Subject previously has entered this study or has been previously exposed to AMG 986.
210. Women who are lactating/breastfeeding or who plan to breastfeed while on study through 11 weeks after receiving the dose of study drug.
211. Men with partners who are pregnant or planning to become pregnant while the subject is on study through 11 weeks after receiving the dose of study drug.
212. QTc Interval:
 - Group 1 (Severe Renal Impairment): QTc > 470 msec or history/evidence of long QT syndrome.

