 - Group 2 (Normal Renal Function): QTc > 450 msec or history/evidence of long QT syndrome.
213. Planned elective surgery within 30 days of study completion or before return of red blood cell parameters to normal values.
214. Blood donation \geq 500 mL within 60 days of day 1.
215. Heart rate \geq 100 beats per minute after 5 minutes of rest or an untreated symptomatic bradyarrhythmia within 1 month prior to enrollment.
216. Unwilling or unable to abstain from nicotine or tobacco containing products (including but not limited to: snuff, chewing tobacco, cigars, cigarettes, pipes or nicotine patches) throughout the screening period and for the duration of the study.
217. Unwilling or unable to abstain from alcohol consumption from 24 hours prior to admission to the research facility (day -1) and throughout the duration of the study.
218. Known history of drug or alcohol abuse within last 12 months.
219. Subjects with a positive drug and alcohol screen at screening or day -1
220. Currently receiving treatment in another investigational device or drug study or less than 30 days or 5 half-lives (whichever is longer) since ending treatment on another investigational device or drug study(s) prior to receiving the dose of investigational product (AMG 986).

Approved

221. Concurrent use of any medications (over-the-counter or prescription) within 14 days or 5 half-lives (whichever is longer) prior to dose of AMG 986, except acetaminophen (up to 2 g per day) for analgesia, hormone replacement therapy (eg, estrogen, thyroid), and medications used to treat CKD and other chronic comorbidities in subjects with severe renal impairment. Continued use if applicable, will be reviewed by the Principal Investigator and the Amgen Medical Monitor. Written documentation of this review and Amgen acknowledgment is required for subject participation.
222. Concurrent or prior use of strong CYP3A4 inhibitors within 14 days or 5 half-lives (whichever is longer) of study day 1, including (not limited to): macrolide antibiotics (eg, clarithromycin, telithromycin), antifungals (eg, itraconazole, voriconazole), antivirals (eg, ritonavir, saquinavir, indinavir, nelfinavir), nefazodone.
223. Concurrent or prior ingestion of grapefruit or grapefruit products and other foods that are known to inhibit CYP3A4 within 7 days of study day 1.

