7.2.14 Electrocardiogram (ECG)

Electrocardiograms (henceforth referred to as electrocardiogram or ECG) will be performed using a standard electrocardiogram machine at the times shown in the Schedule of Assessments.

ECGs will be collected as follows:

With the exception of the Screening ECG, which will be performed as a single electrocardiogram, all ECGs should be performed in a standardized method, in triplicate, and approximately 30 seconds apart, prior to blood draws or other invasive procedures.

At screening a single ECG will be performed. At predose (day 1), ECGs will be performed on 3 occasions separated by at least 30 minutes all in triplicate for a total of 9 ECGs (3 sets of triplicate). At all other time points, ECGs will be performed in a standardized method, in triplicate, and approximately 30 seconds apart, prior to blood draws or other invasive procedures.

Subject must be in a semi-Fowler position in a rested and calm state for at least 5 minutes before the electrocardiogram is obtained. If the subject is unable to be in the semi-Fowler position, the subject should be in the most recumbent position possible.

The electrocardiogram must include the following measurements: PR, RR, QRS, and QTc intervals.

The Principal Investigator or designated site physician will review all ECGs. Once signed, the original ECG tracing will be retained with the subject's source documents. At the request of the sponsor, a copy of the original ECG will be made available to Amgen.

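### Do the unequal QTc entry limits and the loosely named QT correction make the by-group table of maximum post-baseline ECG values misleading?

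*SAP*

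**What the plan says.** SAP 9.6.4 plans two categorical ECG tables by group. One is for change: "Subjects' maximum change from baseline in QTcF will be categorized and the number and percentage of subjects in each group will be summarized". The other is for absolute values: "Subjects' maximum post-baseline values will also be categorized and the number and percentage of subjects in each group will be summarized". The second sentence names no measure; QTcF is a natural reading from the sentence before it. Neither sentence gives category boundaries. Protocol 10.4.3.1.3 has the same two sentences. Baseline is the mean of nine pre-dose tracings on day 1.

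The entry limits differ by group (protocol 4.2, exclusion 212): "Group 1 (Severe Renal Impairment): QTc > 470 msec or history/evidence of long QT syndrome" and "Group 2 (Normal Renal Function): QTc > 450 msec or history/evidence of long QT syndrome". The protocol glossary defines QTc as "qt interval corrected for heart rate using accepted methodology" and lists QTcF separately as the Fridericia correction. Protocol 7.2.14 requires: "The electrocardiogram must include the following measurements: PR, RR, QRS, and QTc intervals".

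Shift tables appear only for laboratory data, and only as an option: "Shift tables based on CTCAE grading may be provided for select analytes". SAP 9.4 summarises baseline ECG parameters for both groups. SAP 3.2 rules out formal hypothesis testing and gives 6 subjects per group.

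**The concern.** The secondary objective compares safety in renal impairment with safety in matched controls, so the table of maximum values will be read across groups. Matching is on age, weight, gender and race, not on QTc. A renal impairment subject may enter at 460 ms and a control may not. If a category began above 450 ms, that subject would count as a high post-dose value without any drug effect, and would move the group by 1/6, or 17 points.

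The unnamed correction adds to this. The analysis names QTcF for change, while eligibility and the required measurements say only QTc. If sites used different corrections, one numerical limit would admit different subjects at different sites. A faster heart rate could also look like QTc lengthening under one correction and not under another. Protocol 2.3 says that effects "such as tachycardia or even hypertension cannot be excluded".

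Finally, the SAP does not say whether post-dose triplicates are averaged before the maximum is taken. Using single tracings would raise the maximum.

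**Working it through.** The plan states no figure for these tables, so there is none to reproduce.

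**Inputs from the documents.** Entry limits 470 and 450 ms, and heart rate below 100 bpm (exclusions 212 and 215); 6 per group (SAP 3.2); ten scheduled post-dose ECG times (protocol Table 2: 1, 2, 4, 6, 24, 48, 72, 96 and 120 h, and end of study).

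**Assumptions.** No drug effect; within-subject SD of a triplicate mean 5, 8 or 10 ms; category boundaries of 450, 480 and 500 ms; baseline population mean 410 to 440 ms with SD 20 ms.

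**1. Where the limits can act alone.** A subject counts if the maximum exceeds boundary c. Only for 450 ≤ c < 470 can the limits place a renal impairment subject, but not a control, above c before dosing. Even this needs the entry QTc to be on the same scale as the analysed value.

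**2. One subject.** P(max > c) = 1 − Φ((c − baseline)/SD)^10.

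| Baseline (ms) | c (ms) | SD 5 | SD 8 | SD 10 |
|---|---|---|---|---|
| 430 | 450 | 0.00 | 0.06 | 0.21 |
| 440 | 450 | 0.21 | 0.67 | 0.82 |
| 460 | 450 | 1.00 | 1.00 | 1.00 |
| 450 | 480 | 0.00 | 0.00 | 0.01 |
| 470 | 480 | 0.21 | 0.67 | 0.82 |
| 470 | 500 | 0.00 | 0.00 | 0.01 |

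For example, at baseline 440, SD 10 and c = 450: 1 − Φ(1)^10 = 1 − 0.8413^10 = 0.82.

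**3. Groups that differ only in the limit.** Simulated baselines come from one population, truncated at 470 or 450 ms.

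- Share above 450 ms: the smallest gap is 5.3% against 3.4% (mean 410, SD 5), or 2.0 points before rounding. The largest is 41.7% against 21.0% (mean 440, SD 5), or 20.6 points before rounding. In a group of 6 that is 6 × 0.020 = 0.1 to 6 × 0.206 = 1.2 subjects.
- Share above 480 ms: at most 5.9% against 0.1% (mean 440, SD 10), or 6 × 0.058 = 0.3 subjects.
- Share above 500 ms: below 0.1% in both.
- Share with change above 30 ms: 0.0% to 1.4% in both, whichever limit applies.

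The absolute-value gaps would be larger if baselines in renal impairment were truly longer.

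**4. The correction.** Bazett divided by Fridericia is RR^(−1/6), with RR = 60/heart rate in seconds, so QTcF = Bazett QTc × RR^(1/6). If the entry QTc were Bazett:

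| Heart rate (bpm) | QTcF for limit 450 | QTcF for limit 470 |
|---|---|---|
| 50 | 463.9 | 484.5 |
| 60 | 450.0 | 470.0 |
| 80 | 428.9 | 448.0 |
| 99 | 414.0 | 432.4 |

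At 50 bpm a control could enter with QTcF of 463.9 ms. The asymmetry in step 1 is therefore not absolute once the correction is left open. The 9-tracing baseline may also lie above a limit that was checked on the single screening tracing.

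If heart rate rises from 65 to 80 bpm with QTcF fixed at 420 ms, Bazett shows 420 × (1.0491 − 1.0134) = 15.0 ms. The categorised change table is in QTcF and would show 0. Only the over-time QTc summary could be affected.

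**5. Replicates.** In simulation, the mean maximum from single tracings exceeds that from triplicate means by 3.9 to 5.8 ms if the assumed SD pairs, (6, 4) to (10, 6) ms, are between-time and between-replicate. It is 6.3 to 10.7 ms if the pairs are reversed. The documents give no SDs. Averaging at each time point is the natural choice, because baseline is itself an average of triplicates.

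**The case for a change.** The strongest case for a change is that it is cheap. A few sentences would name QTcF, state the categories, average the replicates and cross-tabulate the maximum against the baseline category. Safety relative to controls is the secondary objective, one subject is 17 points, and an eligibility decision made under one correction cannot be remade at analysis.

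The facts in this stand. The limits differ, the table has no baseline split, and QTc is not tied to one formula. What does not stand is that a conclusion depends on them.

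- The documents give no boundary between 450 and 470 ms, so the main effect is conditional.
- A cross-tabulation of 6 subjects per group would be mostly empty cells. It would show little beyond the baseline summary, the change table and the individual ECG data.
- Mixed corrections across sites are an assumption that no passage supports. The list in protocol 7.2.14 is a minimum and includes RR. The same section keeps the original tracings with the source documents, so QT can be read if it was not captured.
- Protocol 2.3 reports no ECG abnormalities in the 72 subjects of the first-in-human study and calls the QTc risk low.

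The unnamed correction in exclusion 212 is loose wording. It bears on who enters. It does not bias the change in QTcF after dosing.

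**Conclusion.** No change to the plan is needed. The absolute-value table can show a difference that predates dosing: 2.0 to 20.6 points if a 450 ms boundary is used, at most about 6 points at 480 ms, and practically nil at 500 ms. These sizes rest on assumed boundaries, SDs and baseline distributions. The difference would not mislead a careful reader. The adjacent table of change in QTcF is baseline-adjusted, baseline ECG values are shown by group, all ECG data are reviewed, and no test or decision rule uses the count.

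The category boundaries, the measure in the maximum-value sentence and the averaging of triplicates can be settled sensibly when the tables are programmed. The switch between QTc and QTcF across exclusion 212, protocol 7.2.14 and SAP 9.6.4 is an inconsistency of terms; no view is taken here on the entry limits themselves.
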